6.1 General Principles

Continuous variables will be summarised by the standard descriptive statistics: number of subjects (n), mean, standard deviation, median, minimum, and maximum.

Statistical Analysis Plan

Sponsor Name: Bridge Biotherapeutics, Inc.
Sponsor Protocol ID: BBT401-UC-005

Frequency of subjects or events and percentages will be summarised in categorical variables.

All data processing, summarization and analyses will be performed using Labcorp's SAS Environment / Version 9.4 (or later) of the SAS® statistical software package.

The following principles will be applied to all TFLs unless otherwise stated:

Principle	Value	Suggested Alternative Values
Significant tests	The significance testing will be performed and the 95% confidence interval will be reported where applicable.	
Treatment group labels and order presented	
• 800 mg BBT-401-1S QD and placebo QD• 800 mg BBT-401-1S BID• Placebo BID	
• BBT-401-1S QD +Placebo QD• BBT-401-1S BID• Placebo BID
Tables	Data in summary tables presented by phase, assessment and visit (where applicable).	
Listings	All data collected presented by phase, subject, assessment and visit (where applicable), unless otherwise specified	
Descriptive summary statistics for continuous variables	Number of subjects (n), mean, standard deviation (SD), minimum, median, and maximum.	
Descriptive summary statistics for categorical variables	Frequency counts and percentages [n (%)]	
Denominator for percentages	Number of subjects in the analysis population, unless stated otherwise in table shell(s)	
Include "Missing" as category	Demographics and Other Baseline Characteristics only	
Display for 0 percentages	0	
Display to one more decimal place than collected value	Mean Mean Difference Median	
Display to two more decimal places than collected value	Standard Deviation Standard Error Confidence Interval	
Limit of precision for displays	3 decimal places for non-derived variables and 5 decimal places for derived variables	
Date Format	DDMMYYYY	

CONFIDENTIAL

Page 12 of 30

Statistical Analysis Plan

Sponsor Name: Bridge Biotherapeutics, Inc.
Sponsor Protocol ID: BBT401-UC-005

For subjects who progress into the extension phase and have achieved clinical remission in the induction phase, subjects will continue with the same treatment in the extension phase. If subjects have not achieved clinical remission in the induction phase, then a treatment will be assigned follows the described in Section 2.2. Data display will be summarised/listed by study phase where it is applicable as subjects may switch treatments between induction phase and extension for the Safety Population.

6.2 Subject Disposition and Data Sets Analyzed

Subject disposition will be listed and summarised and will include the number and percentage of subjects:

- screened
- enrolled
- treated
- included in each study population (ITT, Safety, PK and Per Protocol Population).

The number and percentage of subjects who complete the treatment/study at induction phase and who discontinue early from induction phase including primary reasons for discontinuation, will be presented by treatment group [REDACTED]

Additionally, a separate disposition for the extension will be summarised by treatment group [REDACTED] and will include the number and percentage of subjects:

- enter the extension phase
- treatment received during the extension phase
- early discontinue from extension phase with primary reason
- complete the extension phase

Screen failures will be listed with the reasons for failing the screen.

6.3 Protocol Deviations

All protocol deviations will be listed. In addition, all important protocol deviations will be summarised separately for each phase and by treatment group for the ITT Population.

6.4 Demographics and Other Baseline Characteristics

Demographic and baseline characteristics will be listed and summarised by treatment group for the ITT Population. Standard descriptive statistics will be presented for the continuous variables of:

- age (years) [as collected on the CRF]

Statistical Analysis Plan

Sponsor Name: Bridge Biotherapeutics, Inc.
Sponsor Protocol ID: BBT401-UC-005

- weight (kg)

The total counts and percentages of subjects will be presented for the categorical variables of:

- sex
- race
- ethnicity

6.4.1 Medical History

Medical history will be coded using the Medical Dictionary for Regulatory Activities (MedDRA) [Version 23.1 (or a later version if updated during the study)]. All medical history will be listed, and the number and percentage of subjects with any medical history will be summarised by system organ class (SOC) and preferred term (PT) by treatment group for ITT.

6.4.2 Previous and Concomitant Medications

Medications received prior to or concomitantly with treatment will be coded by Labcorp using the WHODrug Dictionary [Sep2020 B3 (or a later version if updated during the study)], Anatomical Therapeutic Chemical (ATC) Classification codes.

Prior medications and concomitant medications are defined as follows:

Prior medications are taken with a start and stop dates prior to the first dose date and time of treatment.

Concomitant medications are those with a start date on or after the first dose date and time of treatment, or those with a start date before the first dose date of treatment and a stop date on or after the first dose date and time of treatment or ongoing end of study.

If there are missing/partial medication start/end dates, the following rule will be used to determine whether the medication is a concomitant medication:

- If month/year of the start date is after the month/year of Day 1, the medication will be considered as concomitant medication.
- If month/year of the start date is equal or before the month/year of Day 1, and the end date is present, the end date will be used to determine whether the medication is prior or concomitant. If the end date is on or after Study Day 1, the medication will be considered as concomitant medication. Otherwise, if the medication stopped before Study Day 1, then the medication is a prior medication.
- If month/year of the start date is equal to the month/year of Day 1, and the end date is a partial date, the medication will be considered as concomitant medication.

Statistical Analysis Plan

Sponsor Name: Bridge Biotherapeutics, Inc.
Sponsor Protocol ID: BBT401-UC-005

If a medication cannot be classified as "prior" or "concomitant" after applying imputation rules for missing/incomplete dates, it will be classified as concomitant.

Prior medications and concomitant medications will be listed together and summarised by treatment group for the ITT Population.

The number and percentage of subjects using each medication will be displayed together with the number and percentage of subjects using at least one medication within each therapeutic class (ATC-Level 2), chemical subgroup (ATC-Level 4), and generic term.

Medication starting date which is within the induction phase will be summarised under the induction phase. Similarly, a medication starting date which is within the extension phase will be summarised under the extension phase.

6.4.3 Concomitant Procedure

Procedure received concomitantly with treatment will be coded

Concomitant procedures will be documented on the CRF. The number and percentage of subjects using each procedure will be displayed together with the number and percentage of subjects using at least one medication [REDACTED] for each phase and by treatment group for the Safety Population.

6.4.4 Rescue Therapy

Rescue medications and rescue procedures are both considered as rescue therapy for this study. Both rescue medication and rescue procedure will be documented on the CRF.

6.4.4.1 Rescue Medication

Rescue medication will be coded by Labcorp using the WHODrug Dictionary [Version Sep2020 B3 (or a later version if updated during the study)], ATC Classification codes.

The number and percentage of subjects using each therapy will be displayed together with the number and percentage of subjects using at least 1 medication within each therapeutic class (ATC-Level 2), chemical subgroup (ATC-Level 4), and generic term for each phase and by treatment group for the Safety Population.

Statistical Analysis Plan

Sponsor Name: Bridge Biotherapeutics, Inc.
Sponsor Protocol ID: BBT401-UC-005

6.4.4.2 Rescue Procedure

Rescue procedure will be coded by Labcorp using the Medical Dictionary for Regulatory Activities (MedDRA) [Version 23.1 (or a later version if updated during the study)].

The number and percentage of subjects with any rescue procedure will be summarised by system organ class (SOC) and preferred term (PT) for each phase and by treatment group for the Safety Population.

6.5 Measurements of Treatment Compliance

Percentage compliance is calculated as:

Overall Compliance:

$100 * \text{actual dose (capsules) taken} / \text{expected dose (capsules) administered}$

The expected dose administered is defined as number of days * 8 (capsules). Where number of days is calculated as the last treatment date – the first treatment date +1.

Compliance under Induction Phase:

$100 * \text{actual dose (capsules) taken} / \text{expected dose (capsules) administered}$

The expected dose administered is defined as number of days * 8 (capsules). Where number of days is calculated as the last treatment date – the first treatment date +1 during the induction phase.

Compliance under Extension Phase:

$100 * \text{actual dose (capsules) taken} / \text{expected dose (capsules) administered}$

The expected dose administered is defined as number of days * 8 (capsules). Where number of days is calculated as the last treatment date – the first treatment date +1 during the extension phase.

Percentage compliance will be summarised descriptively for each study phase by treatment group for the Safety Population. A pooled overall percentage compliance

CONFIDENTIAL

Page 16 of 30

Statistical Analysis Plan

Sponsor Name: Bridge Biotherapeutics, Inc.
Sponsor Protocol ID: BBT401-UC-005

will also be summarised descriptively by induction assigned treatment for the Safety Population.

The number and percentage of compliant subjects will be presented for each study phase by treatment group and pooled overall labelled by induction assigned treatment for the Safety Population, where compliant is defined as percentage compliance between 80.0% and 120.0% inclusive. The following percentage compliance categories will also be presented for overall and each study phase:

- <80.0%
- 80.0% - 120.0%
- >120.0%

6.6 Efficacy

6.6.1 Primary Efficacy Analysis

The primary efficacy endpoint is the clinical response rate at Day 57, as measured by a reduction of ≥ 3 points and $\geq 30\%$ improvement from baseline of total Mayo score, which includes a decrease in rectal bleeding subscore of ≥ 1 point or an absolute rectal bleeding subscore ≤ 1 . Centrally read Mayo endoscopic subscores will be used to evaluate the objectives of the study.

The stool frequency and rectal bleeding subscores will use the average of the last 3 non-missing assessments recorded in the subject diary. If an endoscopy is performed, the average of the last 3 non-missing assessments recorded in the subject diary prior to bowel preparation should be used. If the subscore is not an integer, the subscore should be rounded to the nearest integer. Subjects with missing values will be considered as unresponsive as described in Section 5.2.

Total Mayo Score will be calculated based on the response achieved from all 4 subscores ranged from 0-3 each out of a total sum of 12.

For example: If stool frequency = 2, rectal bleeding = 1, physician's global assessment = 2 and findings on endoscopy = 2 then total mayo score is 7 ($2+1+2+2=7$).

The percentage of improvement at day 57 is calculated as:

$((\text{Baseline Sum of the Total Mayo Score} - \text{Day 57 Sum of the Total Mayo Score}) / \text{Baseline Sum of the Total Mayo Score}) \times 100\%$.

Subjects with a reduction of ≥ 3 points and $\geq 30\%$ improvement from baseline of total Mayo score as well as a decrease in rectal bleeding subscore of ≥ 1 point or an absolute rectal bleeding subscore ≤ 1 will be considered as slowing a clinical response at Day 57.

Statistical Analysis Plan

Sponsor Name: Bridge Biotherapeutics, Inc.
Sponsor Protocol ID: BBT401-UC-005

The number and proportion of subjects with the 95% confidence interval (CI) of clinical response rate at Day 57 will be calculated using the exact binomial method for each treatment. The Fisher's exact test will be used to evaluate any differences between treatments at Day 57 and will be summarised for the induction phase by treatment group for the ITT Population. No adjustments will be made for multiple comparisons.

6.6.2 Secondary Efficacy Analysis

Centrally read Mayo endoscopic subscores will be used to evaluate the secondary objectives of the study.

The stool frequency and rectal bleeding subscores will use the average of the last 3 non-missing assessments recorded in the subject diary. If an endoscopy is performed, the average of the last 3 non-missing assessments recorded in the subject diary prior to bowel preparation should be used. If the subscore is not an integer, the subscore should be rounded to the nearest integer. Missing values will be considered as unresponsive as described in Section 5.2.

- **Clinical remission at Day 57, as measured by a total Mayo score of ≤ 2 points, with no individual subscore exceeding 1 point.**

Total Mayo Score will be calculated based on the response achieved from all 4 subscores ranged from 0-3 each out of a total sum of 12.

Subjects who have a sum of total Mayo score ≤ 2 points, with no individual subscore exceeding 1 point at Day 57, will be considered as achieving clinical remission.

The number and proportion of subjects with the 95% confidence interval (CI) of clinical remission rate at Day 57 will be calculated using the exact binomial method for each treatment. The Fisher's exact test will be used to evaluate any differences between treatments at Day 57 will be summarised for the induction phase by treatment group for then ITT Population.

- **Achievement of endoscopic remission at Day 57, as measured by a Mayo endoscopic subscore of 0 or 1.**

The number and proportion of subjects achieving endoscopic remission at Day 57 with the 95% CI will be calculated using the exact binomial method for each treatment. The Fisher's exact test will be used to evaluate any differences between treatments at Day 57 will be summarised for the induction phase by treatment group for the ITT Population.

- **Change from baseline to Day 57 in the Total Mayo score.**

Statistical Analysis Plan

Sponsor Name: Bridge Biotherapeutics, Inc.
Sponsor Protocol ID: BBT401-UC-005

Analysis of covariance (ANCOVA) with change from baseline as the dependent variable and baseline value as the covariate variable will be used to compare the change from baseline to Day 57 in the total Mayo score between each treated group and the placebo group. The 95% CI for the treatment differences in the change from baseline will be calculated, and the p-value will be provided.

The normality assumption will be checked through the Shapiro-Wilk test of the residuals from the ANCOVA. If the normality assumption is violated at the 0.01 level of significance, an additional nonparametric analysis [REDACTED] [REDACTED] will be used to compare each treated group to the placebo group.

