5.6. Rescue Therapy

A rescue treatment is defined as any procedure or medication (new medications or medications that have been increased in dose) used for the treatment of new or persistent symptoms of UC.

If a subject who does not exhibit a clinical response experiences worsening of disease (ie, worsening of clinical status or symptoms of UC that require rescue treatment) or disease relapse, study drug must be discontinued, and subjects should be treated as clinically appropriate with conventional treatments for active disease, as determined by the investigator. These subjects should continue in the study for safety assessments but will be considered treatment failures with respect to the intent-to-treat population.

A subject will be considered to have disease relapse when they meet all of the following criteria:

- an increase in UC disease activity after achievement of a clinical response, defined as an increase from nadir or Day 57 in partial Mayo score of ≥ 2 points and an absolute partial Mayo score ≥ 4 points, and
- an endoscopic subscore of ≥ 2 points, and
- exclusion of other causes of increased disease activity that are unrelated to UC (eg, infections or changes in medication).

The date and time of rescue medication administration as well as the name and dosage regimen of the rescue medication must be recorded.

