7.5. Guidelines, Study Assessments, and Procedures During the Coronavirus Disease-19 Pandemic

In view of the coronavirus disease -19 (COVID-19) worldwide pandemic, the safety and wellbeing of study subjects is of primary importance. Study sites must comply with local public health rules.

Although every effort should be made to follow the protocol, subject safety is paramount and the investigator should continue to reassess the risks and benefits of continued study participation for each subject.

If a subject is diagnosed with COVID-19 or is suspected to have COVID-19, they should follow the local treatment and quarantine guidances.

- All diagnoses, procedures, assessments, dosing interruptions, and sequelae should be recorded in the electronic case report form (eCRF).
- Adverse events and SAEs should be reported in accordance with instructions in [Appendix 1](#). If an AE or SAE related to COVID-19 is reported, the investigator should determine whether study drug administration should continue, be interrupted, or stopped.

If a subject is unable to attend study site visits and/or receive study drug, site staff should keep contact with the subject, preferably via telephone calls, to maintain awareness of subject status. If the subject is unable to attend the site, the following options may be considered:

- Subjects may be visited at their home by study staff or other trained professionals (where possible due to social distancing requirements).
- Visits may be performed by telephone or telemedicine to provide continuous medical care and oversight and to identify AEs.

- Blood samples may be collected and analysed at an alternative healthcare facility, at the discretion of the investigator. Although results of these analyses may not necessarily be collected or documented in the study database, it will allow the investigator to assess subject safety.
- If the endoscopy at the end-of-treatment visit can not be performed, the partial Mayo score may be collected by telephone or telemedicine (preferred).

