8.4. Efficacy Analyses

8.4.1. Primary and Secondary Efficacy Analysis

All subjects in the intent-to-treat population will be included in the primary and secondary efficacy analyses. Descriptive summaries will be presented for clinical response, clinical remission, and endoscopic remission rates. The estimate and 95% confidence interval (CI) of clinical response, clinical remission, and endoscopic remission rates at Day 57 will be calculated using the exact binomial method for each treatment. The Fisher's exact test will be used to evaluate any differences between treatments.

Missing data will be deemed as "unresponsive". If any event that was not initially anticipated demands to reconsider data handling, then the method of handling the relevant data will be established in the statistical analysis plan.

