4.1 Intent-to-treat Population

The intent-to-treat (ITT) population will include all subjects who receive at least 1 dose of study drug, and who have a partial Mayo score recorded on Day 1 and at least 1 post-baseline Mayo score recorded. Subjects are categorized in the treatment group to which they are randomized.

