5.2 Handling of Dropouts, Missing Data, and Outliers

For the primary and secondary efficacy responder analysis based on the total Mayo score, subjects with missing data will be deemed as "unresponsive". For subjects who received rescue therapy after the first dose of study drug and prior to Day 57, the response status will be deemed as "unresponsive" regardless of the Mayo score value at Day 57.

In terms of the exploratory endpoints, for the endoscopic response rate by total Mayo score, if a subject has no Mayo endoscopic subscore on Day 57, then the last post-baseline measurement prior to Day 57 will be used and the analysis will be based on the imputed value. If a subject does not have any post-baseline Mayo endoscopic subscore measurement, then the subject will be deemed as "unresponsive".

For modified Mayo remission rate at Day 57, if a subject has more than or equal to 2 questions are not answered, then the subject will be considered as "unresponsive". If a subject has only 1 question is not answered, then the last post-baseline question answered prior to Day 57 will be used to calculate the modified Mayo remission rate at Day 57.

For systemic remission rate at Day 57 based by total Mayo score, if a subject has 2 questions are not answered, then the subject will be considered as "unresponsive". If a subject has only 1 question is not answered, then the last post-baseline question answered prior to Day 57 will be used to calculate the systemic remission rate at Day 57.

For the clinical remission at Day 112, the percentage of subjects with sustained remission on Day 112, and the clinical response rate at Day 112 which are all based on the total Mayo score, if a subject has more than or equal to 3 questions are not answered, then the subject will be considered as "unresponsive". If a subject has less than 3 questions are not answered, then the last post-baseline question(s) answered prior to Day 112 will be used to calculate the total Mayo score and information relevant to derive those Day 112 related exploratory endpoints.

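### The ANCOVA of Day 57 change in total Mayo score has no visible rule for rescued subjects, so a recorded post-rescue score would count as an ordinary outcome despite the protocol's treatment-failure rule

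*SAP*

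**What the plan says.** SAP 6.6.2 (Secondary Efficacy Analysis), last bullet: "Analysis of covariance (ANCOVA) with change from baseline as the dependent variable and baseline value as the covariate variable will be used to compare" each active group with placebo on change in total Mayo score, with a 95% CI and a p-value. SAP 7 (Changes in Planned Analysis) records that the study team added this endpoint. The bullet itself names no analysis population and gives no rule for rescue.

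SAP 5.2 holds the data-handling rules. Its missing-data sentence opens "For the primary and secondary efficacy responder analysis based on the total Mayo score". The next sentence deals with rescue before Day 57: it sets the subject's response status to non-response "regardless of the Mayo score value at Day 57". The lead-in to SAP 6.6.2 adds: "Missing values will be considered as unresponsive as described in Section 5.2".

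Protocol 5.6 (Rescue Therapy) stops study drug in these subjects and says: "These subjects should continue in the study for safety assessments but will be considered treatment failures with respect to the intent-to-treat population". Protocol 8.4.1 says: "All subjects in the intent-to-treat population will be included in the primary and secondary efficacy analyses".

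SAP 5.1 analyses data by nominal visit, without windows. In the induction part of the Protocol Appendix 11 schedule, the total Mayo score is collected only at screening and at Visit 5, which serves both as the Day 57 end-of-treatment visit and as the early-termination visit.

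**The concern.** Non-response is a usable value for a rate but not for a change score. The SAP carries the protocol's failure rule into the responder endpoints and then adds a continuous endpoint on the same scale without carrying the rule across. A rescued subject whose Visit 5 score has fallen because of the rescue treatment would be a failure in the primary analysis and an improver in the ANCOVA, with that improvement credited to the randomised arm.

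This is the only secondary endpoint for which the SAP plans an estimated difference from placebo with a confidence interval; the other three Day 57 rate analyses, one primary and two secondary, give per-arm exact intervals and Fisher tests. With 12 subjects per arm, the handling of one or two subjects is visible in that estimate. If no rule is fixed beforehand, the choice may be made once results by arm are known.

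**Working it through.** **Does any visible text supply a number?**

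- SAP 5.2, primary and secondary endpoints: limited to the responder analysis; the rescue sentence sets response status only.
- SAP 5.2, carry-forward rules: assigned to exploratory endpoints. They could not help here, because induction has no earlier post-baseline total score to carry forward.
- SAP 6.6.2 lead-in: a label that points back to 5.2.
- SAP 6.6.3 (Sensitivity Analysis): the rules are redacted, but the introductory sentence restricts them to the clinical response and clinical remission rates.
- SAP 6.6.2, redaction after the normality check: it sits where the nonparametric method is named.

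So no visible rule applies to the ANCOVA. That the model would then use whatever Visit 5 holds is an inference from the nominal-visit rule and ordinary complete-case fitting; the SAP does not say so.

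**How much could it matter?** The documents give no effect size, SD, rescue rate or power, so there is no planned figure to reproduce. From the documents: 12 per arm. Assumed: mean change of −3 (active) and −2 (placebo) in non-rescued subjects, balanced baselines, r rescued subjects per arm, and mean recorded post-rescue change v.

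Arm mean = [(12 − r) × m + r × v] / 12, with v = 0 for the failure value.

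Shift in the difference, as observed minus zero change = (r_active × v_active − r_placebo × v_placebo) / 12.

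| Rescued, active/placebo | Post-rescue change, active/placebo | Difference, zero change | Difference, as observed | Shift |
|---|---|---|---|---|
| 1/3 | −3/−3 | −2.75 − (−1.50) = −1.25 | −3.00 − (−2.25) = −0.75 | +0.50 |
| 3/1 | −3/−3 | −2.25 − (−1.83) = −0.42 | −3.00 − (−2.08) = −0.92 | −0.50 |
| 2/2 | −3/−3 | −2.50 − (−1.67) = −0.83 | −3.00 − (−2.17) = −0.83 | 0 |
| 2/2 | −2/−5 | −0.83 | −2.83 − (−2.50) = −0.33 | +0.50 |
| 1/3 | +1/+1 | −1.25 | −2.67 − (−1.25) = −1.42 | −0.17 |

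If the rescued subjects have no Visit 5 total score they drop out, and the difference is −3 − (−2) = −1.00 in every row. That does not count them as failures either.

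Rows 1 and 2 show that the shift can go either way. Row 4 shows a shift with equal rescue counts. Row 5 reverses the direction seen in row 1 because the rescued subjects stay worse than baseline.

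For an imbalance of two and equal improvement after rescue, the shift is 2 × improvement / 12 in absolute size: 0.33, 0.50 and 0.83 points for improvements of 2, 3 and 5 points.

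**Against the precision available.** Assume one model on 36 subjects with three arms and one covariate, which leaves 32 degrees of freedom. Half-width = t(0.975, 32) × SD × √(2/12), which is 1.66 points for SD 2 and 2.49 for SD 3 (SDs assumed). The ratios run from 0.33/2.49 = 0.13 to 0.83/1.66 = 0.50.

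**Cross-check.** A simulated ANCOVA (2,000 runs, 12 against 12) used different assumptions: SD 2.5, mean change −4 active and −2 placebo, and −4 after rescue. With 1 active and 3 placebo rescued, the mean estimate was −1.40 as recorded and −2.06 with zero change. With 3 active and 1 placebo, it was −1.77 and −1.10. The shifts of +0.66 and −0.67 agree with the formula, which gives ±8/12 = ±0.67.

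**The case against.** **A post-rescue score may never exist.** Protocol 5.6 keeps these subjects for safety follow-up, and Visit 5 doubles as the early-termination visit. A score recorded there might precede any effect of rescue and already show failure. This stands as a limit: such scores are possible, not established. But the SAP 5.2 wording quoted above expects that a Day 57 Mayo score may exist after rescue, and nothing keeps it out of the ANCOVA.

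**The protocol prescribes no number.** True. Protocol 8.4.2 planned only descriptive summaries of change in Mayo scores, and the ANCOVA came with the SAP. The conflict is with the protocol's principle, not with a prescribed value. Still, Protocol 5.6 does not confine the failure rule to rates.

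**Missing scores.** A reader might infer that dropping non-rescued subjects without a Visit 5 total also breaks the protocol. Such subjects are foreseeable: ITT entry needs only "at least 1 post-baseline Mayo score recorded", and Protocol 7.5 says "If the endoscopy at the end-of-treatment visit can not be performed, the partial Mayo score may be collected by telephone or telemedicine". But Protocol 5.6 concerns rescue only, the non-response convention in Protocol 8.4.1 sits with analyses of rates, and including all ITT subjects does not by itself prescribe imputation. SAP 5.2 openly leaves missing biomarker data unimputed. The partial Mayo MMRM in SAP 6.6.5 can also use scores collected by telephone, although it too shows no rescue rule. This is a separate missing-data matter.

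**Direction.** A reader might infer that as-observed scoring always favours the arm with more rescue and is harmless when rescue is equal. That holds only if post-rescue changes are improvements with the same mean in both arms.

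**Population.** The bullet's silence is not a real gap, because Protocol 8.4.1 puts secondary analyses in the ITT population. Naming it in the SAP only confirms this.

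**Conclusion.** The point holds for rescued subjects. As visible, the ANCOVA would count any recorded post-rescue score as an ordinary outcome, while Protocol 5.6 counts the subject as a treatment failure. In the scenarios with an imbalance of two, the shift is at most about half of the confidence-interval half-width. That rests wholly on assumed rescue counts, post-rescue scores, arm means and SDs, and the documents fix neither the size nor the sign.

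Severity is minor. The study is exploratory with no formal sample-size basis, the primary analysis already handles rescue, and SAP 6.4.4 tabulates rescue by phase and treatment group. Parts of the SAP are redacted or were not available, so the finding is that no visible rule exists. Confidence is medium.

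**What to change.** State in SAP 5.2 and 6.6.2:

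- The ANCOVA of change in total Mayo score uses the ITT population.
- A subject who receives rescue therapy after the first dose and before Day 57 is assigned zero change from baseline, or the change at a pre-rescue early-termination assessment if that is worse.
- The as-observed analysis is reported as a sensitivity analysis, and the numbers rescued and the numbers without a Visit 5 total score are shown by arm beside the estimate.

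For non-rescued subjects with no Visit 5 total score, report the number by arm and show zero change only as a sensitivity analysis. As the main rule it would treat a missed endoscopy as no benefit even where the partial score had improved.

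The cost is a few SAP sentences and the extra sensitivity runs. The downside is that a fixed failure value is a convention: a rescued subject may have improved by a point or two beforehand, the worse-of clause works in one direction only, and a cluster of zeros slightly distorts the residuals. The result also depends on whether an early-termination endoscopy was done: with 1 active and 3 placebo rescued, the difference is −1.25 without one and −1.42 if each shows a change of +1. The as-observed run shows how much the convention matters.
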